on "Promoting Self-Care in Persons with Heart Failure" identified the importance of determining the operative mechanisms of effective tele-health and self-management strategies.¹⁰⁸⁻¹¹⁰ While ENABLE improved QOL, mood, and in some cases survival,⁶³ the operative mechanisms of these effects had not yet been fully explored. Our proposal directly addresses this issue. As depicted in Figure 1a, we hypothesize, based on the CIC model^{111,112} that the intervention may have relatively immediate effects on patients' behaviors (activation, goal setting, problem solving, follow-up /coordination, and decision support) and adoption of these behaviors may operate as proximal mediators and have more distal effects on patients' sense of social support and coping. Ultimately, these proximal and distal intervention effects are hypothesized to serve as the mechanisms whereby the intervention improves patients' QOL and reduces depression, anxiety, and perceived symptom burden. Evidence for these mechanisms has been found in studies of patients in rural primary care,¹¹³ HF⁵⁵ and others.^{114,115} Resultant improved communication and advance care planning has also been associated with improved QOL, lower use of aggressive treatments at EOL, and increased hospice length of stay.¹¹⁶⁻¹²² Increased social support¹²³⁻¹²⁵ and coping style¹²⁶⁻¹²⁸ have been associated with improved cardiac patients' well-being. To our knowledge no studies have prospectively addressed caregiver intervention mechanisms. Figure 1b illustrates hypothesized caregiver, patient, and reciprocal interactions.¹²⁹ Examining these relationships may potentially identify mutable factors for future caregiver intervention targets.^{130,131}

A8 This proposal addresses the knowledge gap related to longitudinal analysis of palliative care data.

Miaskowski^{132,133} and others at the NINR-sponsored summit, “*Science of Compassion: Future Directions in End-of-Life and Palliative Care*” made a plea for the use of increasingly sophisticated statistical analysis methods for longitudinal palliative care patient data. Our group has implemented innovative analysis methods in our previous work⁶³ and we will continue to develop these methods in the HF population (See [name] and Li consultant LOS/biosketches).

B INNOVATION

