determining the profile characteristics (e.g. race, SES, gender, military vs. civilian background, absence of caregiver, etc.) of the participants who benefited the most and the least from the intervention using flexible modeling techniques, such as latent class analysis and recursive partitioning.

Specific Aim 2 Caregiver QOL, mood, self-reported health, burden

Caregiver outcomes will be analyzed using the same longitudinal methods as outlined for Specific Aim 1. For the analyses going forward in time from baseline, the effects of patient death on caregiver outcomes will be examined using models with indicators for patient death at its respective time-point. Only decedents' caregivers will have grief outcomes analyzed which will not involve longitudinal modeling. Caregivers of patients who die will contribute the additional outcome of a rating of quality of care at the end of life (QODD). Since only one QODD observation will be available for each decedent, no longitudinal modeling is required. However, analysis of these measures will be conducted with mixed effect methods to account for nesting, with the parameter of interest being the association between group assignment and the caregiver-rated outcome

Exploratory Aim 1. Explore mediators/moderators of patient/caregiver outcomes and reciprocal relationships.

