As depicted earlier in Figure 1a, intervention effect on patient QOL, mood, and symptom burden is proposed to be mediated by the quality of chronic illness care (PACIC), active and avoidant coping styles (COPE), social support (MSPSS) and health literacy (NVS). This conceptual logic will be tested using structural equation modeling (SEM) applied to matrices residualized for demographic and disease factors.¹⁸⁹ Each patient model will involve 13 observed variables: the intervention as a dichotomous variable, five mediational variables (8 week: PACIC, active COPE, avoidant COPE, MSPSS, NVS) lagged against their five baseline values, and the 8 week outcome of interest lagged against its baseline. With 22 degrees of freedom, a sample size of 359 (expected to be alive/available at week 8), and a significance level of $p = .05$, power is .86 to distinguish a model with close fit (root mean square error of approximation [RMSEA] = .05) from a model with mediocre to poor fit (RMSEA = .09).¹⁹⁰ Jointly significant effects involving the theorized mediators (intervention → mediator, mediator → outcome as depicted in Figure 1a) will constitute evidence of mediation. Assuming a medium effect size ($d=0.5$) on mediator and outcome, a sample size of 359 provides .80 power to detect a small indirect effect of at least 34% of the total intervention effect size ($d_M=0.17$) based on computer simulations of joint tests with a significance level of 0.05.¹⁹¹

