As depicted earlier in Figure 1b, the effect of the intervention on caregiver QOL, mood, and burden is proposed to be mediated by patient well-being. Tests of mediation of caregiver outcomes will involve jointly significant ($p = .05$) effects (intervention → 8 week patient outcome → 24 week caregiver outcome) for caregiver outcomes mediated by patient outcome. Assuming a medium effect size ($d=0.5$) on both mediator and outcome, a sample size of 188 (expected CGs with 24 week outcomes) provides .80 power to detect an indirect effect size of at least 48% of the total intervention effect size ($d_M=0.24$) based on computer simulations of joint tests with a significance level of 0.05.¹⁹¹ As depicted earlier in Figure 1b, the effect of the intervention on caregiver QOL, mood, and burden is proposed to be mediated by patient well-being. Tests of mediation of caregiver outcomes will involve jointly significant ($p = .05$) effects (intervention → 8 week patient outcome → 24 week caregiver outcome) for caregiver outcomes mediated by patient outcome. Assuming a medium effect size ($d=0.5$) on both mediator and outcome, a sample size of 188 (expected CGs with 24 week outcomes) provides .80 power to detect an indirect effect size of at least 48% of the total intervention effect size ($d_M=0.24$) based on computer simulations of joint tests with a significance level of 0.05.¹⁹¹

Exploratory Aim 2. Examine intervention effects using joint modeling approaches.

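### Exploratory Aim 1 names reciprocal patient-caregiver relationships, but only the patient-to-caregiver path is tested, and significance on that path alone does not settle the direction

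*Combined protocol and SAP*

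**What the plan says.** The heading of Exploratory Aim 1 in C5.2 reads "Explore mediators/moderators of patient/caregiver outcomes and reciprocal relationships". Section A7 describes the underlying conceptual model in the same terms: "Figure 1b illustrates hypothesized caregiver, patient, and reciprocal interactions".

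The analysis text under the aim has two parts.

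- **Patient outcomes.** A structural equation model: "Each patient model will involve 13 observed variables: the intervention as a dichotomous variable, five mediational variables". The remaining variables are the five mediators' baselines and the patient outcome at week 8 and baseline. No caregiver variable is listed.
- **Caregiver outcomes.** Here "the effect of the intervention on caregiver QOL, mood, and burden is proposed to be mediated by patient well-being". The test requires both links of one chain to be significant: "intervention → 8 week patient outcome → 24 week caregiver outcome) for caregiver outcomes mediated by patient outcome". This paragraph is printed twice in identical words, and neither copy contains a caregiver-to-patient path. It lists no covariates.

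Nothing elsewhere supplies the reverse direction. The patient-death indicators under Specific Aim 2 also run from patient to caregiver. The only caregiver feature applied to patient results is the absence of a caregiver, as a subgroup characteristic under Specific Aim 1. No cross-lagged or other two-way dyadic model is described.

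**The concern.** There are two separate problems.

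1. **The plan leaves part of its own aim unanswered.** A reciprocal relationship cannot be examined by fitting one direction.

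2. **The one-way test can mislead.** Randomisation protects the link from arm to week-8 patient outcome. It does not protect the link from week-8 patient outcome to week-24 caregiver outcome. Caregivers have their own four-session curriculum (C3), so by week 8 they may have changed in response to it. That change could move the patient at week 8 and carry forward to the caregiver at week 24. The footnote to the patient criteria in C2.2 accepts that caregiver support can affect heart failure outcomes. The gap between weeks 8 and 24 orders mediator before outcome but does not remove a common cause already present at week 8. Adjusting for baselines does not remove it either, because it arises after randomisation.

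At stake is the wording of a mechanism claim. A7 says that examining these relationships may help to identify targets for later caregiver interventions, and B2 stresses understanding mechanisms. Crediting the patient when the caregiver sessions did some of the work would point that follow-up in the wrong direction.

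**Working it through.** **The plan's own figure.** C5.2 gives power 0.80 with 188 caregivers, d = 0.5 on mediator and outcome, and an indirect effect of 0.24, "based on computer simulations of joint tests with a significance level of 0.05". Taken literally, path a is a two-group comparison with 94 per arm and d = 0.5. The noncentrality is 0.5 × √(94/2) = 3.43, giving power 0.929. Path b is 0.24/0.5 = 0.48, with power 1.000. The joint power is 0.929 × 1.000 = 0.929 (0.930 by simulation). Reading 0.24 as a correlation on each path gives 0.853 analytically and 0.829 by simulation. I could not reproduce 0.80. The simulation model is not given, so this does not show the figure to be wrong, and nothing below depends on it.

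**Inputs for the check.** From the documents: 188 dyads and the 0.05 level (C5.2), 1:1 allocation (C2.3), and within-person correlation 0.5 (C5.3), used here as the carry-over. Assumed, because the documents give no values: caregiver effect 0.5 SD at week 8, baseline dyad correlation 0.3, caregiver-to-patient slope κ, direct patient effect δ, and two-sided tests.

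**Model with no patient-to-caregiver path** (X = arm, each e independent standard normal):

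- P0 = 0.3·C0 + √0.91·e
- C8 = 0.5·C0 + 0.5·X + √0.75·e
- P8 = 0.5·P0 + δ·X + κ·C8 + √0.75·e
- C24 = 0.5·C8 + √0.75·e
- P24 = 0.5·P8 + κ·C8 + √0.75·e

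Patient mediation is declared when the arm is significant for P8 (given P0) and P8 is significant for C24 (given arm and both baselines). Every declaration is false by construction. There were 3,000 replicates per row.

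| δ | κ | One-way test, both baselines | One-way test, week-8 caregiver score added | Reverse path found |
|---|---|---|---|---|
| 0 | 0.1 | 0.8% | 0.3% | 26% |
| 0 | 0.2 | 2.4% | 0.5% | 74% |
| 0 | 0.3 | 8.8% | 0.7% | 94% |
| 0.3 | 0.1 | 7.6% | 3.6% | 28% |
| 0.3 | 0.2 | 17.9% | 4.3% | 73% |
| 0.3 | 0.3 | 38.4% | 4.4% | 95% |

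Repeat runs gave 1-8% for the first three rows and 7-38% for the last three. The simulation standard error for the 8.8% entry is √(0.088 × 0.912/3000) = 0.5 percentage points, so the runs agree.

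**Reading the table.**

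- With δ = 0 the arm reaches the patient only through the caregiver, with effect κ × 0.5, at most 0.3 × 0.5 = 0.15 SD. The first link is therefore rarely significant (7%, 13% and 20% of trials in the three rows), which keeps the false rate low.
- With κ = 0 and δ = 0.5 the one-way test gives 5.2%, so the excess comes from the stated mechanism.
- Without baseline adjustment, which the caregiver paragraph does not mention, the six rates are 1.5%, 5.5%, 14.0%, 16.9%, 39.7% and 62.8%.
- With carry-over 0.7 and both baselines they are 1.2%, 5.1%, 14.1%, 10.5%, 35.9% and 66.1%.
- The reverse path is harder to find if the caregiver effect is smaller. Across caregiver effects of 0.3 to 0.5 SD and κ of 0.2 to 0.3, it was found in 48-94% of trials.

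**The opposite truth.** Now let the arm act on the patient only, let the patient's change move the caregiver by week 8, and let that carry to week 24. Patient mediation is then real. Adding the week-8 caregiver score cut its detection from 31-82% to 3-6%, roughly the false-positive level. With a further lagged patient effect of 0.1, detection was 55-99.8% without the score and 16-25% with it.

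**The case against.** The strongest objection is the last calculation. The tempting remedy is to replace the planned test with a cross-lagged model that conditions on the week-8 caregiver score. That would exchange one misattribution for its opposite, because the score may itself lie on the true path from patient to caregiver. Two follow-up waves cannot establish direction when influence passes within the first eight weeks. This stands, and it shapes the fix.

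Three further points also stand.

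- **Size.** A reader might infer that the planned test misattributes in a large share of trials. The documents give no caregiver-to-patient slope. When the effect is purely caregiver-driven and the slope modest, the rate is close to or below the nominal level; the higher rates mostly need a genuine direct patient effect as well.
- **Model content.** A reader might infer that the plan leaves the week-8 caregiver score out. The caregiver paragraph lists no covariates, so the supportable statement is that the model is not specified.
- **Sources.** Figure 1b and the opening of the document were not available for this check. The repeated paragraph may be a copying slip where the reverse test was meant to stand, or an artefact of text extraction. This cannot be settled from the text.

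The aim is exploratory, and A7 is hedged about what the results may contribute. That limits the importance of the point but does not remove the gap between the aim and its analysis.

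**Conclusion.** The point holds as a gap in an exploratory aim. The text names reciprocal relationships and specifies one direction, and its joint-significance rule can credit the patient for a link that is partly or wholly the caregiver's own early response. With 188 dyads, both baselines, carry-over 0.5 and slopes of 0.1 to 0.3, the false attribution rate is about 1-8% with no direct patient effect and about 7-38% with a 0.3 SD patient effect. These ranges rest on assumed effects and should be read as illustrations of sensitivity, not as forecasts for this trial.

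Two stronger conclusions are not supported: that the planned path is invalid and should be discarded, and that adjusting for the week-8 caregiver score would identify the true direction. Primary and secondary comparisons are unaffected. The change is worth making because it is cheap and lets the trial address the question it sets itself.

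**What to change.** 1. Keep the planned path and list its covariates, including both baselines.
2. Add the reverse path: arm to week-8 caregiver score to week-24 patient outcome, given week-8 patient score, both baselines and arm.
3. Report the patient-to-caregiver path twice, without and with the week-8 caregiver score in the week-24 caregiver equation. Adding the reverse path alone would not protect against misattribution.
4. State the reading rule in advance. Claim mediation by the patient without qualification only if it holds in both versions. If it holds only without the week-8 caregiver score, report the direction as unresolved, because that adjustment also removes any true patient effect that had reached the caregiver by week 8.

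The cost is SAP wording and analysis time. Patient and caregiver outcomes are already scheduled at baseline, week 8 and every 8 weeks to week 48 (Table 3), so no new data are needed. The downside is one more indirect effect and one more model per outcome, with more cautious wording of an exploratory result.

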	Caregiver burden	Montgomery Borgatta Caregiver Burden Scale (MBCB) ¹⁸¹	Measure of caregiver burden with 3 domains: objective burden, stress burden, and demand burden; 14 items	Subscales α = .75 to .88	
	Self-reported health	PROMIS SF Global Health ¹⁰	2 domains: physical and mental health, 10 items	Subscales α = .81 to .86	
Exploratory Aims					
HF Patients	Patient Activation	Patient Assessment of Chronic Illness Care (PACIC) ¹⁸²	5 dimensions: activation, delivery system/decision support, goal setting, problem solving, and coordination; 20 items	Subscales α =.62 to .90	Baseline, week 8 and every 8 weeks until week 48
	Coping style	Brief Cope	2 subscales: active and avoidant coping; 28 items ¹⁸³	α = .68 to .79	
	Social support	Multidimensional Scale of Perceived Social Support (MSPSS)	Perceived adequacy of support from family and friends, 12 items ¹⁸⁴	α =.81	
All	Health literacy	Newest Vital Sign ⁹	Measure of health literacy and numeracy based on interpretations of a nutrition label, 6 items	α = .76	Baseline only
	Demographics	Demographic questionnaire	Age, gender, race, marital status, religion, employment, education, occupation, health insurance, smoking, etc.	NA	

Additional measures and data

If patients die on study we will conduct a standardized interview with a study or non-study (if agreeable) caregiver 2 months after death using the instruments and similar techniques from prior studies^{129,185} to evaluate the caregivers' perception of the EOL care provided and to assess their grief experience and mood. The questionnaires are: 1) proxy-reported Quality of Death and Dying (QODD) (31-items) which rates the quality of the descendant's last 7 days; it has acceptable internal consistency (Cronbach alphas 0.89) and construct validity;^{186,187} 2) Inventory of Complicated Grief-Short form (ICG-SF) a reliable, validated 13-item survey of complicated grief¹⁸⁸ and the HADS (described above).

C4.1 Data Collection, Management, and Quality Control.

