Data Security: All databases are secure, HIPAA-compliant and password protected in both the front end and back end. Back end data will be housed on a secure drive with access limited to only authorized research personnel.

C5 STATISTICAL CONSIDERATIONS

C5.1 Randomization. After consent and baseline assessment, patients will be randomized using computer-generated treatment assignments, stratified by center (UAB or BVAMC), referring service (HF clinic, cardiology, primary care), and race (Caucasian/non-Caucasian).

C5.2 Statistical Analyses

Specific Aim 1 Patient-reported QOL, mood, symptom burden, and resource use

The intention to treat (ITT) analysis will be used for all treatment comparisons. That is, all randomized patients will be included in primary comparisons, regardless of whether the patient actually received the randomly-assigned intervention. Primary data analysis will begin with descriptive statistics for baseline patient characteristics and outcomes by treatment group. Distributional assumptions will be examined; when appropriate we will employ testing and modeling procedures that do not assume normality. We will compare groups with respect to baseline covariates. We will analyze and compare missing data and compliance patterns according to baseline covariates and we will adjust analyses for baseline factors showing either imbalances or predictive of missing data (not due to patient death) or compliance. Mixed modeling techniques and covariate adjustment will reduce the impact of missing data, provided that the data are missing at random. If necessary, multiple imputation techniques and sensitivity analyses will be used to deal with data not missing at random and not caused by patient death.

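### The patient mediation model needs a week-8 health-literacy score that the schedule does not collect, so health literacy cannot be tested as a mediator; the other four mediators can

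*Combined protocol and SAP*

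**What the plan says.** **The model.** Section C5.2, Exploratory Aim 1, proposes that the intervention's effect on patient quality of life, mood and symptom burden is mediated by chronic illness care, active and avoidant coping, "social support (MSPSS) and health literacy (NVS"). Each patient model has 13 observed variables: treatment arm, "five mediational variables (8 week: PACIC, active COPE, avoidant COPE, MSPSS, NVS) lagged against their five baseline values", and the outcome at week 8 and baseline. The fit-test power statement that follows begins "With 22 degrees of freedom, a sample size of 359 (expected to be alive/available at week 8"). Evidence of mediation is defined as "Jointly significant effects involving the theorized mediators", meaning both the arm-to-mediator and the mediator-to-outcome effects.

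**The schedule.** Table 3 (section C4) gives PACIC, Brief COPE and MSPSS the entry "Baseline, week 8 and every 8 weeks until week 48". The health literacy row, which applies to all participants, describes NVS as based on "interpretations of a nutrition label, 6 items", and its schedule entry is "Baseline only".

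**The order of events.** Section C5.1 states: "After consent and baseline assessment, patients will be randomized using computer-generated treatment assignments".

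**The concern.** The analysis plan and the measurement schedule describe different data sets. The model treats health literacy as something the intervention may have changed by week 8, whereas the schedule measures it once, before assignment. Section B2 presents health literacy as one of the changeable factors through which the intervention is thought to work, so this is a stated hypothesis and not an incidental covariate.

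If the conflict is left alone, the analyst will find one model variable empty and will have to improvise. Dropping NVS without a documented change would abandon that hypothesis silently and leave a variable count, degrees of freedom and power that describe a model nobody fitted. Entering baseline NVS in the mediator position would be worse, because a pre-randomisation score cannot carry a treatment effect.

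**Working it through.** **1. Reproduce the plan's count of 13.** From Exploratory Aim 1:

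- treatment arm: 1
- week-8 mediators (PACIC, active COPE, avoidant COPE, MSPSS, NVS): 5
- baseline values of the same mediators: 5
- outcome at week 8 and at baseline: 2

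1 + 5 + 5 + 2 = 13, as printed. The total is reached only if week-8 NVS is counted, so its appearance in the list is not a stray word.

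**2. Set the count against Table 3.**

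| Mediator | Baseline | Week 8 |
|---|---|---|
| PACIC | yes | yes |
| Active COPE | yes | yes |
| Avoidant COPE | yes | yes |
| MSPSS | yes | yes |
| NVS | yes | not scheduled |

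The number of variables with scheduled data is 1 + 4 + 5 + 2 = 12 if baseline NVS is kept, or 1 + 4 + 4 + 2 = 11 if NVS is removed altogether.

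**3. Look for a later NVS elsewhere.** Section C3.1 provides for telephone data collection at week 8 and every 8 weeks to week 48, but names no instruments. No other section of the supplied text schedules NVS after baseline.

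**4. Ask whether baseline NVS could stand in.** Mediation requires both an arm-to-mediator and a mediator-to-outcome effect. Since baseline precedes randomisation, any difference between arms in baseline NVS is chance. The first path therefore has no estimate that bears on the intervention, and the joint test cannot be met.

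**5. Ask whether the missing-data methods could help.** Section C5.2 allows mixed models, covariate adjustment and multiple imputation. These work when some participants have the value. Here no participant would have a week-8 NVS, so there is nothing to inform the imputation.

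**6. Check the fit-test power printed beside the model.** Inputs from Exploratory Aim 1 are df = 22, N = 359, alpha = .05, null RMSEA .05 and alternative RMSEA .09. The test uses a noncentral chi-square with noncentrality (N − 1) × df × RMSEA².

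- Null: 358 × 22 × .05² = 19.69, giving a 95th-percentile critical value of 61.30.
- Alternative at exactly .09: 358 × 22 × .09² = 63.80, giving power 0.932.
- Alternative at .085: 358 × 22 × .085² = 56.90, giving power 0.860.

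The printed power is .86. It does not follow from .09 taken exactly, but it does follow from .085, which would appear as .09 at the two decimals shown.

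**The case against.** **It is only exploratory.** This is true, and it limits the weight of the point. Four of the five mediators are measured as the model requires. The caregiver mediation model runs from the intervention through the week-8 patient outcome to the week-24 caregiver outcome and does not use NVS. The primary analyses and Table 4 do not depend on it. A reader might infer that the whole mediation analysis fails; the schedule does not support that, because a reduced model with the other four mediators has all its data.

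**The Table 3 entry may not be specific to NVS.** It stands on the first row of the block for all participants, and the demographics row below has a blank schedule cell, so it may be one merged cell covering both. On the natural reading it still covers NVS.

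**Not everything is available.** Figure 1a and the instrument appendix are not in the supplied text. They might show which passage is the slip, but they would not remove the conflict between Table 3 and section C5.2.

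**The printed power looks wrong.** A reader might infer this, since the printed inputs taken exactly give 0.932 and not .86. The documents do not establish an error, because rounding of the alternative RMSEA could account for the whole gap. The documents do not confirm that explanation either. Any discrepancy would be conservative, and it is not part of this point.

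**Adding NVS at week 8 may be impractical by telephone.** A nutrition-label task is awkward in a phone call, but the documents do not show it to be infeasible. Section C4.1 says that collecting most data through the electronic health record is being explored, and section C3 already has materials mailed to intervention participants.

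**Conclusion.** The conflict is real and needs no power figure to establish it. The 13-variable, 22-df patient model requires a measurement that the supplied schedule does not provide. The intervention-to-NVS path cannot be estimated, and health literacy cannot be tested as a patient mediator.

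The size is one of 13 variables and one of five mediators, within the patient part of an exploratory aim. It should be corrected before analysis, but it does not threaten the trial's main conclusions.

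The conclusion assumes that the schedule in Table 3 is the one followed and that no unsupplied material adds a later NVS. The documents do not say whether the table or the model is the slip. The degrees of freedom of a reduced model cannot be derived from the text, because the free paths are not listed and Figure 1a is not shown.

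**What to change.** Reconcile Table 3 with Exploratory Aim 1 before analysis. The choice is the sponsor's.

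**Preferred: change the model.** Remove NVS from the mediators and use baseline NVS as a moderator or covariate, which the aim's title already covers since it names moderators as well as mediators. Restate the variable count (12 with baseline NVS kept, 11 without), the degrees of freedom and the fit-test power for the reduced model, giving the alternative RMSEA to enough decimals for the power to be reproduced. This costs a few lines of analysis-plan wording and one recalculation. The downside is that the health-literacy mediation hypothesis is given up, and section B2 should then say so.

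**Alternative: change the schedule.** Add the six-item NVS for patients at week 8 and keep the 13-variable model. This costs a protocol schedule change and one added task at a follow-up planned as phone-based, including a way to show the patient the nutrition label. It can help only patients who have not yet passed week 8, since a missed measurement cannot be recovered.

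### The patient mediation rule takes mediators and outcome from the same week-8 visit, so, as specified, it does not separate mediation from the reverse path or from shared week-8 variation

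*Combined protocol and SAP*

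**What the plan says.** The patient model in C5.2, Exploratory Aim 1, contains the intervention and "five mediational variables (8 week: PACIC, active COPE, avoidant COPE, MSPSS, NVS) lagged against their five baseline values". The variable to be explained comes from the same visit: "and the 8 week outcome of interest lagged against its baseline". Here lagging means adjustment of each variable for its own baseline; no time passes between mediator and outcome. The decision rule is: "Jointly significant effects involving the theorized mediators (intervention → mediator, mediator → outcome as depicted in Figure 1a) will constitute evidence of mediation". No later outcome, reverse path, cross-lagged path or sensitivity analysis is given for the patient model, although the aim's title mentions reciprocal relationships.

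Three other places bear on this:

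- A7 describes an ordered process in which "adoption of these behaviors may operate as proximal mediators and have more distal effects on" social support and coping, with quality of life and mood improving at the end of the chain.
- The caregiver model in the same aim separates the times: "8 week patient outcome → 24 week caregiver outcome".
- Table 3 collects the patient outcomes, PACIC, Brief COPE and MSPSS at "Baseline, week 8 and every 8 weeks until week 48", but schedules the Newest Vital Sign (NVS) at baseline only.

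**The concern.** A patient who feels better at week 8 may, for that reason, rate care, coping and support more highly. Anything that colours all self-report scales at one interview has a similar effect. Either can make both planned paths significant when the mediator does nothing to the outcome. Baseline adjustment removes stable differences between patients, but not reverse or shared change that arises between baseline and week 8.

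B2 presents this aim as the route to the intervention's active ingredients. A false positive would direct later intervention design to the wrong component.

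**Working it through.** **1. The plan's own figure.** C5.2 states power 0.80 at N = 359 for an indirect effect of 34% of the total, "Assuming a medium effect size ($d=0.5$) on mediator and outcome", based on "computer simulations of joint tests with a significance level of 0.05". No formula is given. Treating the two paths as independent, each with d = 0.34, reproduces it: z = 0.34 × √(359/4) = 3.22; Φ(3.22 − 1.96) = 0.896; 0.896² = 0.803. This is power when the one-way model is true. It says nothing about how often the rule succeeds when there is no mediation.

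**2. Inputs for the false-positive check.** From the documents: d = 0.5, significance level 0.05 (taken as two-sided), intra-subject correlation 0.5 (C5.3), and N = 356 at week 8, 334 at week 16 and 313 at week 24 (Table 4). Assumed: linear normal data with unit variance, baseline mediator-outcome correlation 0.3, and the reverse-path and residual-correlation values below.

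**3. Reverse-path truth.** Y8 = 0.5·arm + 0.5·Y0 + e and M8 = b·Y8 + 0.5·M0 + e, each e with variance 1 − 0.5² = 0.75. M never affects Y. With both baselines in both equations:

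- Arm to mediator: effect 0.5b, standard error 2·√(0.75(1 + b²))/√356.
- Mediator to outcome: t ≈ b·√351, with 356 − 5 = 351 degrees of freedom.

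| b | z, arm to mediator | chance significant | chance, mediator to outcome | joint | simulated |
|---|---|---|---|---|---|
| 0.1 | 0.54 | 0.08 | 0.46 | 4% | about 4% |
| 0.2 | 1.07 | 0.19 | 0.96 | 18% | 17–19% |
| 0.3 | 1.57 | 0.35 | about 1 | 35% | 35% |
| 0.5 | 2.44 | 0.68 | about 1 | 68% | 68–70% |

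If each equation adjusts only for its own baseline, simulation at N = 359 (2,000 trials per setting) gives 3%, 17%, 34% and 66%. With d = 0.3 instead, it gives 2%, 10%, 15% and 29%. With no reverse path the rate is 0.1–0.2%.

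**4. Shared-variation truth.** The arm moves both variables by 0.5, M does not affect Y, and the week-8 residuals correlate r. Arm to mediator is almost always significant: z = 0.5/(2·√0.75/√356) = 5.4. For mediator to outcome, t ≈ √351·r/√(1 − r²): 1.88 at r = 0.1 (chance 47%) and 3.82 at r = 0.2 (97%). Simulation gives 48% and 97% with both baselines in each equation, or 36% and 92% with own baseline only.

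**5. Lagged alternative.** Keep M8, move the outcome to week 16 and adjust it for its baseline and week-8 values. Under either truth M8 then has no remaining association with Y16, so the second path is a true null and the joint rate cannot exceed about 5%. Simulation at N = 334 gives about 0.5–3% under the reverse path and 4–6% under shared residuals.

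**6. What the lagged test loses.** If mediation is complete by week 8 and nothing further passes to week 16, the second path is again null. The lagged test then detects true mediation in about 5% of trials, against 96–100% for the same-visit test. Power rises to about 12–17% at a further lagged path of 0.05, 45–50% at 0.10 and 75–80% at 0.15. It is lower where mediator and outcome are tightly linked at week 8. Falling numbers matter less: step 1 repeated at N = 334 gives z = 3.11 and power 0.76; at N = 313, z = 3.01 and 0.73.

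**7. Does the fit check protect?** Not reliably. A one-way 13-variable reconstruction fitted to reverse-path data has population RMSEA of 0.04–0.06, around the plan's close-fit value of 0.05. That version has 30 degrees of freedom against the stated 22; Figure 1a is not shown, so the planned paths cannot be matched exactly.

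**The case against.** The strongest case on the other side has four parts.

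- **Early action is plausible.** A7 expects fairly immediate effects on behaviour. If the mediator has already acted by week 8, adjusting for the week-8 outcome removes the effect being sought. This stands: step 6 shows the cost, and it rules out simply replacing the planned model.
- **The magnitudes are conditional.** They come from single-mediator regressions, not the five-mediator SEM on residualized matrices, and no document supplies a reverse path or residual correlation. This also stands. At a reverse path of 0.1 the false rate is only 3–4%, so the figures show what the rule permits, not what it will do in this trial.
- **The SEM is not inherently unable to separate directions.** A reader might infer that no week-8 model could. That is too strong: a two-way model using the baselines as instruments could in principle estimate both directions. The criticism applies to the one-way rule that C5.2 states.
- **The aim is exploratory.** Joint significance is called evidence, not proof. True, but the rule still attaches the word mediation to a pattern that other explanations produce.

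Two further inferences should be avoided. The caregiver model is not a complete template: it separates the times, but its text mentions no adjustment for the baseline or week-8 caregiver outcome. Nor does Table 3 provide every measure 8-weekly, because NVS is baseline only. Week 8 is not immediately after the curriculum either. On the C3.1 schedule session 6 falls around days 36–42, two to three weeks before day 56.

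**Conclusion.** The concern holds for the rule as specified. With no mediator effect, it declares mediation in about 4%, 17% and 70% of trials at reverse paths of 0.1, 0.2 and 0.5. The rates are about 48% and 97% at week-8 residual correlations of 0.1 and 0.2 (36% and 92% with own-baseline adjustment only). A lagged test holds this near or below 5%. These sizes rest on d = 0.5, linear normal data, one mediator at a time and assumed path values.

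The consequence is confined to conclusions about mechanism. A reader might infer that the trial's main results are at risk; they are not, because the primary intention-to-treat comparisons do not use this model. Nor do the documents show that a positive mediation result would be false, only that the stated rule could not tell. This should be corrected before the exploratory analysis is run.

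**What to change.** 1. Keep the week-8 same-visit model, but label its mediator-outcome path as an association.
2. Add a lagged model: week-8 mediators to the week-16 or week-24 outcome, adjusted for the baseline and week-8 values of that outcome, or a cross-lagged SEM over the 8-weekly visits. Require it to support the path before mediation is claimed.
3. State that the lagged model tests further change after week 8, and that a null result does not rule out mediation complete by then.
4. Restate N and power for the lagged model at 334 (week 16) or 313 (week 24) from Table 4, and reconcile the 359 in C5.2 with Table 4's 356 for week 8.
5. Reconcile NVS between C5.2 and Table 3. On data already collected it can enter as a baseline covariate or moderator, but not as a week-8 mediator.

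For the outcomes and the mediators other than NVS, the cost is analysis-plan wording and one extra model, with no new data collection. Keeping NVS as a week-8 mediator would require adding an assessment. The statistical cost is the limited power for early mediation shown in step 6 of the working.
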